## 5.10. Study Termination

Study termination is defined as the time when all study treatments, study-specific assessments, and study data collection are completed. Upon termination of the study, the Sponsor or designee will conduct site closure activities with the Investigator or site staff (as appropriate), in accordance with applicable regulations.

The Sponsor reserves the right to temporarily suspend or terminate the study at any time for reasons including, but not limited to, safety issues or ethical reasons. The Sponsor or designee will also promptly inform the relevant regulatory authorities of the suspension/termination along with the reasons for such action, when applicable. Where required by applicable regulations, the Investigator or head of the medical institution must inform the IRB/EC.

## 6. SAFETY PARAMETERS, DEFINITIONS, AND REPORTING

Safety assessments will consist of monitoring and recording AEs, serious AEs (SAEs), non-serious AESIs listed in [Section 5.3.2](#); performing protocol-specified laboratory assessments; measuring -protocol-specified vital signs; and conducting other protocol-specified tests that are deemed critical to the evaluation of ME-401.

The Investigator will assess AEs for severity and relationship to study drug and determine if an AE meets the criteria for an SAE. Each AE will be graded in the source documents using NCI CTCAE v5.0.

All AEs observed within 30 days after study drug last dose should be reported recorded. All SAEs will be reported for up to 90 days after the last dose of study drug. All SAEs that are deemed related to the study drug must be reported even if beyond 90 days after last dose of study drug, if they become known to the investigator. All deaths should be reported and communicated to the sponsor or designee. Death not due to disease progression should be reported as an SAE. Death associated with disease progression is not an SAE.

### 6.1. Adverse Event (AE)

An AE is any untoward medical event that occurs in a subject following the start of study drug administration, whether or not the event is considered drug-related (ICH Guideline E6 §1.2).

An AE can therefore be any of the following:

- A pre-existing medical condition can be recorded as an AE if the condition worsens by at least one grade following the start of study drug administration and if the frequency, severity, or character of the condition worsens during the study. When recording on the eCRF it is important to capture applicable descriptors (e.g., more frequent arthritic pain).
- Disease-related out-of-range laboratory values will not be considered AEs/SAEs if there is no change from the screening laboratory values. Any deterioration in a laboratory value or other clinical test that is associated with symptoms, or leads to a change in study

treatment or concomitant treatment, or discontinuation from study product, or deemed clinically significant by the Investigator will be considered an AE.

Adverse events will be recorded using the terminology defined in the NCI CTCAE v5.0.

Adverse events will be captured from the time of the first dose of study drug on Cycle 1 Day 1 and continue until 30 days after the last dose of study drug.

Any TEAE of Grade 2 or higher should be followed for resolution until either:

- The start of subsequent anti-cancer therapy
- Death

A TEAE is defined as an AE starting after the first dose until 30 days after the last dose of study drug.

Death related to disease progression is not considered an AE. Signs and symptoms related to disease progression are not considered AEs. Anticipated fluctuations of pre-existing conditions, including the disease under study that do not represent a clinically significant exacerbation or worsening, are not considered AEs.

Only one AE term should be recorded in the event field on the AE eCRF if a specific AE is attributable to a primary diagnosis. Adverse events that are secondary to other events should be identified by their primary cause, with the exception of severe or serious secondary events.

For example:

- If a subject initially had diarrhea and is subsequently diagnosed with colitis, this event should be consolidated to one event, colitis
- If a subject had diarrhea that resulted in mild dehydration, only diarrhea should be reported in the eCRF
- If a subject who had diarrhea developed acute renal failure, both acute renal failure and diarrhea should be reported in the eCRF

For AEs, a diagnosis should be recorded on the AE eCRF rather than individual signs and symptoms (e.g., record only colitis rather than diarrhea, abdominal pain, decreased appetite). However, if a constellation of signs and symptoms cannot be medically characterized as a single diagnosis or syndrome, each individual event should be reported on the AE eCRF. If a diagnosis is subsequently established, all previously reported AEs based on signs and symptoms should be nullified and replaced on the AE eCRF based on a single diagnosis, with a starting date that corresponds to the starting date of the first symptom of the eventual diagnosis.

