**Table 4: ME-401 Toxicity Management (Continued)**

Toxicity	Grade*	Management of ME-401	Management of Toxicity
Cutaneous Reactions and Mucositis	2	
 
Hold ME-401 unless rash ascertained to be unrelated to study drug.
 
If ME-401 is held, once AE resolves to Grade <math>\leq 1</math>, resume ME-401 at 60 mg administered on the IS.
 
	
 
Monitor subjects and determine cause of rash.
 
Per Investigator's discretion, antihistamines, topical steroids, and systemic steroids may be given.
 

	<math>\geq 3</math>	
 
Hold ME-401 until AE resolves to Grade <math>\leq 1</math>, then, if clinically indicated, resume ME-401 at 60 mg administered on the IS.
 
For recurrence of Grade 3, permanently discontinue ME-401.
 
	
 
Monitor subjects as clinically indicated until resolution.
 
Oral antihistamines and systemic corticosteroids such as prednisone 0.5–1 mg/kg/day (or equivalent dose of methylprednisolone) should be given until rash resolves to Grade <math>\leq 1</math>.
 

	Any	
 
Permanently discontinue ME-401 for life-threatening toxicity, Stevens-Johnson syndrome of any grade, and TENS of any grade.
 
	
 
Treat per institutional standard of care.
 

Hepatotoxicity	2	
 
For ALT/AST <math>>3-5 \times</math> ULN but <math><5 \times</math> ULN, maintain ME-401 treatment dose and schedule.
 
	
 
Monitor ALT/AST weekly until resolved to Grade <math>\leq 1</math> or baseline level.
 

	3	
 
For ALT/AST <math>>5-20 \times</math> ULN, hold ME-401.
 
Resume ME-401 at 60 mg administered on the IS.
 
For recurrence of Grade 3, permanently discontinue ME-401.
 
	
 
Monitor ALT/AST once a week until resolved to Grade <math>\leq 1</math> or baseline level.
 
Treat per institutional standard of care, which may include a course of corticosteroids if clinically indicated.
 
Assess if Hy's law applies.
 

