### 5.3.2. Adverse Events of Special Interest (AESIs)

In this study, the following are considered AESIs:

- Cutaneous reactions, including skin rash Grade  $\geq 2$  (see [Appendix 3](#) for guidance for toxicity assessment)
- Oral mucositis or stomatitis Grade  $\geq 2$
- Diarrhea/colitis Grade  $\geq 2$

- It is important to differentiate infectious diarrhea from non-infectious diarrhea, as treatment and management of subjects will depend on the identified cause (see [Table 4](#) for management of non-infectious diarrhea). To confirm suspected colitis, utilize colonoscopy or diagnostic methods as per institutional standards.
- AST/ALT Grade  $\geq 2$
- Non-infectious pneumonitis (NIP) of any grade
- Lung infection/pneumonia Grade  $\geq 2$
- Cardiomyopathy of any grade

Refer to [Table 4](#) for ME-401 Toxicity Management.

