### **3.3.2. Incidence Rate of Adverse Event of Special Interests (AESIs)**

The rate of AESIs is calculated as the proportion of subjects with at least one AESI.

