#### **8.3.2. Adverse Events of Special Interest (AESI)**

AESIs are events of scientific and medical interest specific to the further understanding of the ME-401 safety profile. For ME-401, AESIs will comprise of (see study protocol [Section 5.3.2](#)):

- Cutaneous reactions, including skin rash Grade  $\geq 2$
- Oral mucositis or stomatitis Grade  $\geq 2$
- Diarrhea/colitis Grade  $\geq 2$
- AST/ALT Grade  $\geq 2$
- Non-infectious pneumonitis (NIP) of any grade
- Lung infection/pneumonia Grade  $\geq 2$
- Cardiomyopathy of any grade

AESI will be summarized by selected subgroups.

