### **8.3.3. Summaries of Incidence of Adverse Events**

The number and percentage of subjects reporting TEAEs and AESIs will be summarized as below:

- Overall summary of TEAEs and AESIs
- TEAEs by SOC and PT
- TEAEs by PT
- TEAEs of Grade 3 and above by PT
- TEAEs by maximum grade and PT
- TEAEs leading to treatment discontinuation by PT
- TEAEs related to ME-401 leading to treatment discontinuation by PT
- TEAEs leading to treatment interruption by PT
- TEAEs related to study drug by PT
- AEs leading to death by PT
- Treatment-related AEs leading to death by PT
- Treatment-Emergent SAEs by SOC and PT
- Treatment-Emergent SAEs by PT
- Treatment-Emergent SAEs by maximum grade and PT
- Treatment-emergent AESIs by AESI Type and PT
- Treatment-emergent Grade 3 and Above AESIs by AESI type and PT
- Covid-19 events by grade
- Other important safety events including opportunistic infection, CMV infection, PJP infection, and fungal infection, cytopenia event, pulmonary event by maximum grade and PT

Selected analysis on TEAEs will be summarized by subgroups.

Listings will be produced for all AEs, TEAEs, SAEs, AEs leading to treatment discontinuation, AEs leading to death, AESI, and for subjects with grade 3 and above AEs.

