#### **8.4. Laboratory Evaluations**

Lab evaluations will include hematology (including coagulation), serum chemistry, urinalysis, pregnancy test, HIV testing, Hepatitis B and Hepatitis C testing, bone marrow aspiration/biopsy, PCR tests for CMV and opportunistic infection (OI) monitoring.

For statistical and graphical summaries of the laboratory tests, values below or above the limit of detection (e.g., '< 3' or '>500') are substituted with the lower limit of detection minus 1% for values below the lower limit and are substituted with the upper limit of detection plus 1% for values above the upper limit (e.g., '< 3' is substituted by '2.97', '> 500' is substituted by '505'). In data listings, the values are shown including the < or > sign.

Results from the hematology, chemistry, and urinalysis will be summarized by visit using descriptive statistics, including the observed values and change from baseline values for numeric parameters and distribution of categories for categorical parameters. Boxplots by visit will be generated for selected hematology/chemistry parameters.

In addition, the incidence rate of grade 3 and above toxicity for selected hematology and chemistry parameters will be summarized by visit. Separate listings will be produced for subjects with grade 3 and above toxicity for selected hematology and chemistry parameters.

Treatment-emergent toxicities are defined as the worsening of lab toxicity grade comparing to the baseline. The incidence rate of treatment-emergent grade 3 and above toxicity for hematology and chemistry parameters will be summarized by visit.

By-subject listings of hematology, serum chemistry, and urinalysis tests, including lab normal ranges, will be provided. Derived CTCAE grades will be included in listings, as applicable.

The following lab data will be listed only: pregnancy test, HIV, Hepatitis B and Hepatitis C tests, bone marrow aspiration/biopsy, CMV titers, and OI monitoring.

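### The AST/ALT Grade ≥2 AESI may be under-counted: it is defined by laboratory grade but appears to be tabulated from AE records, where an asymptomatic Grade 2 rise can depend on Investigator judgement

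*Protocol*

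**What the plan says.** **Definition.** Protocol 5.3.2 ("In this study, the following are considered AESIs") and SAP 8.3.2 ("AESIs are events of scientific and medical interest specific to the further understanding of the ME-401 safety profile") both list AST/ALT Grade ≥2. Neither adds a condition about symptoms or clinical significance, and neither names the data source. Protocol Section 6 names non-serious AESIs, separately from AEs and SAEs, among the things monitored and recorded.

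**When a laboratory change is an AE.** Protocol 6.1: "Any deterioration in a laboratory value or other clinical test that is associated with symptoms, or leads to a change in study", continuing "treatment or concomitant treatment, or discontinuation from study product, or deemed clinically significant by the Investigator will be considered an AE".

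**What happens at Grade 2.** For Grade 2 hepatotoxicity, Protocol Table 4 says "maintain ME-401 treatment dose and schedule". Its toxicity-management column asks only for weekly ALT/AST until recovery.

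**Analysis.** SAP 3.3.2: "The rate of AESIs is calculated as the proportion of subjects with at least one AESI". SAP 8.3.3 lists the table "Treatment-emergent AESIs by AESI Type and PT", and under SAP 8.3 preferred terms are assigned to AEs. SAP 8.4 summarises laboratory toxicity incidence from Grade 3 upward. Below that, "Derived CTCAE grades will be included in listings, as applicable".

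**The concern.** The AESI is a statement about a measured value. The count appears to run on AE records, and the test in 6.1 for when a laboratory value is an AE is not the same as the AESI threshold. For an asymptomatic Grade 2 rise handled as Table 4 describes, the only limb of 6.1 left is the Investigator's view of clinical significance.

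Entry is allowed with AST/ALT up to 3.0 × ULN (inclusion criterion 8), and Table 4 places Grade 2 above 3 × ULN. A small further rise can therefore qualify as an AESI and still be judged not significant by a site.

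AESI incidence and time to first AESI are secondary endpoints, and Protocol 11.2.2 calls for AESI rates with 95% CIs by dosing group. A lower AESI burden is also part of the rationale for the intermittent schedule (Protocol 2.3). If the gap operates, it varies by site and lowers the reported rate.

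**Working it through.** **1. The plan's own AESI figure.** Protocol 11.1 gives 15/120 Grade ≥3 AESIs as 12.5% with 95% CI 7.2–19.8%. The exact Clopper-Pearson limits are the 2.5% quantile of Beta(x, n−x+1) and the 97.5% quantile of Beta(x+1, n−x). With x = 15 and n = 120 these are 7.2% and 19.8%, so the figure reproduces. The other precision statements also reproduce: 5/120 gives 1.4–9.5%, and in SAP 2.4 25/184 gives 9.0–19.4% and 9/184 gives 2.3–9.1%.

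The AESI statements among these concern Grade ≥3 events. At Grade 3 AST/ALT Table 4 holds the drug, and at Grade 4 it discontinues it. Both meet 6.1 through the treatment limbs, so this gap does not reach those figures.

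**2. One case traced through the text.** ALT 4 × ULN at Cycle 3 Day 1, no symptoms, managed per Table 4:

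- Protocol 5.3.2 / SAP 8.3.2: an AESI by grade.
- Protocol Section 6: falls under the recording of non-serious AESIs.
- Protocol 6.1: no symptoms, no change of study treatment, no concomitant treatment called for by Table 4, no discontinuation. Clinical significance is left to the Investigator.
- SAP 8.3.3: counted if there is a coded AE record. No other route is described.
- SAP 8.4: below Grade 3, so it appears in listings only.
- SAP 3.3.3: if it is not counted and there is no other AESI, the subject is censored at data cutoff or at treatment discontinuation.

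**3. Possible size.** The documents give neither the Grade 2 share of transaminase rises nor the share not reported. The following is a scenario range, not an estimate.

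Missed subjects = N × p × s × u, where

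- N = 120 (planned FL subjects on the intermittent schedule, Protocol 11.1);
- p = 11/57 = 19.3% (AST increased, all grades, intermittent group, Protocol Table 2, none Grade 3), taken by assumption as the rate of any rise;
- s = share of those peaking at Grade 2 (assumed);
- u = share of those not recorded (assumed).

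N × p = 120 × 11/57 = 23.2.

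| s | u = 0 | u = 50% | u = 100% |
|---|---|---|---|
| 10% | 0 | 1.2 (1.0 points) | 2.3 (1.9 points) |
| 25% | 0 | 2.9 (2.4 points) | 5.8 (4.8 points) |
| 50% | 0 | 5.8 (4.8 points) | 11.6 (9.6 points) |

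Using the 121 FL subjects enrolled (Protocol 8.3) changes the largest cell only to 11.7. Within each scenario the effect on the overall AESI rate is at most the figure shown, because a subject with another AESI is already counted.

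Three cautions on p. It counts reported AEs, so it shows that low-grade rises were reported in Phase 1b and is no evidence of under-reporting. It is AST only. Protocol Table 3 shows one Grade 3 AST/ALT event in the same group, so the absence of Grade 3 applies to the AST row of Table 2.

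**4. Illustration of scale.** If 30/120 had a recorded AESI (an assumed figure), the rate is 25.0% (95% CI 17.5–33.7%). Adding 6 subjects gives 30.0% (22.0–39.0%), and adding 12 gives 35.0% (26.5–44.2%), if none of those added had another AESI.

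**The case against.** The case that nothing is lost has real weight.

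- Section 6 already says non-serious AESIs are recorded. Nothing in 6.1 says an AESI need not be, so the specific instruction can be read as supplementing the general one.
- The laboratory sentence in 6.1 says which deteriorations count as AEs. It does not say that all others are excluded.
- Section 10 speaks of a Grade 2 AE of transaminase elevation, and Table 4 requires weekly tests. A value that triggers extra protocol testing may usually be judged significant.
- The any-grade AESI rate is descriptive, with no test or decision rule attached, and Grade 2 values stay visible in listings.

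These points rule out the stronger reading that a reader might infer: that an asymptomatic Grade 2 rise fails the AE definition, so that the AESI rate necessarily misses such subjects. The clinical-significance limb and Section 6 both leave a route to capture, and the SAP's reliance on AE records is itself an inference from the preferred-term tables.

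They do not close the gap. The Schedule of Assessments has only an adverse-events row, Protocol 9.5 describes collection of AEs and SAEs only, and no text gives 5.3.2 and Section 6 priority over 6.1. The SAP neither states the source nor checks AE records against laboratory grades.

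**Conclusion.** The concern holds as a risk. Capture of an asymptomatic Grade 2 AST/ALT rise can depend on site judgement, and the SAP has nothing that would detect a missed one. Any resulting error lowers the any-grade AESI rate, and leaves time to first AESI too late or censored.

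The size cannot be computed from the documents. It may be zero; about 0 to 12 of 120 subjects (0 to 9.6 percentage points), before overlap with other AESIs, rests on assumed values of s and u and on using the Phase 1b AST rate as the rate of any rise.

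A reader might also infer that the safety margins in Protocol 11.1 and SAP 2.4 are weakened. They are not: the AESI statements there are for Grade ≥3 events, where Table 4 changes or stops treatment.

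This is a cheap improvement to a secondary endpoint and does not bear on the primary analysis.

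**What to change.** 1. In SAP 3.3.2 and 8.3.2, count the AST/ALT AESI from the earlier of (a) a post-dose local laboratory value, scheduled or unscheduled, within the treatment-emergent period, with derived CTCAE v5.0 Grade ≥2 and worse than baseline, or (b) a reported AE of that type and grade. Use that date in time to first AESI (SAP 3.3.3 and 8.3.4).
2. Show the AE-reported count alongside, so that the result can be set against Phase 1b.
3. In SAP 8.4, add a table of Grade ≥2 AST/ALT laboratory values reconciled to AE records.
4. Reconcile Protocol 6.1 with 5.3.2 and Section 6, so that laboratory values at AESI level are recorded whatever their judged clinical significance.

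Cost: SAP wording and some programming. SAP 8.4 already derives CTCAE grades and defines treatment-emergent laboratory toxicity as worsening from baseline, so no new data are needed and closed enrolment is no obstacle. The AESI rate may come out slightly higher and may include some disease-related rises; showing both counts makes that visible. No clinical management changes.

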## 6.2. Assessment of Severity

The term “severity” is used to describe the intensity of an AE. Severity will be graded according to NCI CTCAE v5.0. For AEs not covered by CTCAE, each AE will be assigned a category by the Investigator as described in [Table 5](#).

**Table 5: NCI CTCAE v5.0 Adverse Event Grading System**

Grade	Comments
1	Mild; asymptomatic or mild symptoms; clinical or diagnostic observations only; intervention not indicated
2	Moderate; minimal, local or noninvasive intervention indicated; limiting age-appropriate instrumental ADL a
3	Severe or medically significant but not immediately life-threatening; hospitalization or prolongation of hospitalization indicated; disabling; limiting self-care ADL b
4	Life-threatening; urgent intervention indicated
5	Death related to AE

Abbreviations: ADL = activities of daily living; AE = adverse event

a. Instrumental ADL refer to preparing meals, shopping for groceries or clothes, using the telephone, managing money, etc.

b. Self-care ADL refer to bathing, dressing and undressing, feeding self, using the toilet, taking medications, and not bedridden.

### 6.3. Action Taken with Study Drug in Response to the AE

The Investigator will record the action taken regarding the study treatment in response to an AE:

- Dose not changed
- Dosing schedule changed from CS to IS
- Drug interrupted
- Drug withdrawn
- Not Applicable
- Unknown

### 6.4. Outcome of AE

The Investigator will record the outcome of the AE as follows:

- Recovered/resolved
- Recovered/resolved with sequelae
- Not recovered/not resolved
- Death
- Unknown

All AEs should be followed until the event has resolved or the condition is stabilized as assessed by the Investigator.

## 6.5. Serious Adverse Event (SAE) Definition

Per ICH Guideline E2A §II.B, an SAE is any untoward medical occurrence (i.e., AE) that at any dose results in any of the following outcomes:

- Death
- A life-threatening condition
- An inpatient hospitalization or prolongation of an existing hospitalization
- A persistent or significant disability/incapacity or substantial disruption of the ability to conduct normal life functions
- A congenital anomaly/birth defect
- Any other medically important event: defined as an event that may jeopardize the subject or may require intervention to prevent one of the outcomes listed above. Medical and scientific judgement must be exercised in deciding whether an event is serious. Any new primary cancer must be reported as an SAE.

The term “life-threatening” in the definition refers to an event in which the subject was at risk of death at the time of the event; it does not include any AE that had it occurred in a more severe form or was allowed to continue might have caused death.

Elective hospitalizations not in response to an AE are not considered SAEs. Hospitalizations related to disease progression are not considered SAEs. A procedure (e.g., surgery) is not an AE in itself, but the reason for the procedure may be an AE. Admission for social reasons, without an underlying medical condition, including hospice, will not be reported as an SAE.

- After informed consent has been obtained and prior to start of study drug, only SAEs caused by a protocol-mandated intervention (e.g., invasive procedures such as biopsies) should be reported (see [Section 6.6](#) for SAE reporting instructions).
- All SAEs will be reported for up to 90 days after last dose of study drug. After 90 days following last dose of study drug, SAEs deemed related to study treatment must be reported to the Sponsor or Sponsor’s designee if they become known to the Investigator.

Severity and seriousness are independent of each other and need to be independently assessed for each AE recorded on the eCRF.

